8.1 General Design

This is a 24 week Phase I/II study of clenbuterol in patients with ALS (Table 3, Section 11). All subjects will be evaluated at Week 0 to establish a baseline and return to be evaluated for safety and efficacy during the Week 4, 12 and 24 visits. The drug will be initiated at the Week 0 visit in a staged manner (first once daily and later BID), and the dose will be increased at the Week 6 visit in a similarly staged manner to minimize AEs and related attrition. All subjects will return for a final visit after a total of 24 weeks in the study.

The initial dose of clenbuterol will be 40 mcg per oral each morning for one week, followed by 40 mcg BID for the next 5 weeks until the week 6 visit. If the 40 mcg BID per oral is well tolerated, the dose will be increased to 80 mcg each morning/40 mcg each evening for one week, followed by 80 mcg BID for the next 5 weeks until the Week 12 visit. If 80 mcg BID is tolerated at Week 12, the subject will continue on that dose until Week 24. The subject will have several phone visits to evaluate safety, tolerability and ALSFRS-R score. These will occur at Week 1, 6, 16, and 20.

The efficacy of clenbuterol administration will be evaluated with the revised ALS Functional Rating Scale (ALSFRS-R) and other secondary endpoints.

8.2 Primary Study Endpoints

The primary endpoint is safety of clenbuterol at 80 mcg BID. Adverse and serious AEs will be systematically gathered as described in section 8 below.

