A previous small open-label pilot trial of clenbuterol in patients with ALS showed very promising results (SORARU *et al.* 2006). Sixteen patients with ALS were started on 60 mcg/day, and fourteen completed 6 months of treatment. Significant improvements in limb muscle strength and forced vital capacity (FVC) occurred in these patients, and a functional measure called the ALS functional rating scale score was stable over the course of the trial. Improvements and stability on these recognized ALS outcome measures are not typical of the natural history of this disease. Again, clenbuterol was found to be safe and well-tolerated (Table 1). The dramatically positive results of this pilot trial need to be replicated.

Table 1: Long-Term Clinical Studies with Clenbuterol

Study	Study Design	Number of Subjects	Dosage and Regimen	Adverse Events
(DI GIOACCHINO et al. 1987)	Open label study of clenbuterol in exercise induced asthma	14 patients	20 mcg bid for 60 days	Small increase in heart rate
(ISHIKO et al. 2000)	Randomized study of clenbuterol and physiological therapy (PT) in stress incontinence	61 patients assigned to three groups A-clenbuterol only B- PT only C - both	20 mcg bid for 12 weeks in 41 patients (group A and C)	1) Two patients with headache 2) One patient with mild hepatopathy 3) One patient with rash 4) One patient with numbness
(SORARU et al. 2006)	6 month open label dosing in patients with ALS already on riluzole	16 patients	20 mcg TID for 6 months	Tremor, nervousness, cramps, fasciculations (details not provided)
(KAMALAKKANNAN et al. 2008)	Single site, randomized, double blind placebo controlled in subjects with class 2 or 3 congestive heart failure	19 subjects -- 10 placebo 9 clenbuterol	20 mcg BID, increased to 40 mcg BID after 7 days – 12 weeks total	1) Two clenbuterol subjects withdrew, one with asymptomatic ventricular tachycardia, and one with muscle cramps without elevated CK 2) Six clenbuterol and two placebo subjects with muscle cramps 3) CK elevated in 5

				subjects on clenbuterol, and in 4 on placebo 4) Tremors in 5 subjects on clenbuterol and two on placebo
(KOEBERL et al. 2018)	52 week double-blind, placebo controlled, prospective study in LOPD patients stably treated with ERT for >1 year	13 randomized, 11 completed	40 mcg for 1 week, 40 mcg BID for 5 weeks, 80 mcg AM + 40 mcg PM for 1 week, 80 mcg BID for 40 weeks	4 subjects with tremor 4 subjects with insomnia 4 subjects with muscle spasms

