6.2 Investigational Agent

ACTIONS AND MODE OR MECHANISMS OF ACTIONS

Clenbuterol is a broncholytic agent which acts through selective stimulation of the β_2 -receptors. It differs from other β_2 -specific sympathomimetics by its low dose, long biological half-life and rapid and complete absorption by oral administration. It has no significant effects on β_1 -cardiac receptors.

PHARMACOLOGY

Pharmacokinetics: Invasion half-life of clenbuterol is 1 hour, and the distribution corresponds to an open two compartment model with a side-compartment. Elimination from plasma takes place in 2 phases, the half-life of the α -phase being 1 hour and that of β -phase 34 hours. Elimination is primarily renal (87% after 168 hours) 43% of clenbuterol is recovered unchanged in the urine. Dose intervals of 12 hours suffice to maintain a plasma level. Five metabolites have been found in humans.

INDICATIONS

Prophylaxis and therapy of bronchospasm in bronchial asthma, acute and chronic bronchitis associated with emphysema.

CONTRAINDICATIONS

Thyrotoxicosis, idiopathic hypertrophic subvalvular aortic stenosis, tachycardia, tachyarrhythmia. Known sensitivity to sympathomimetic amines.

SIDE EFFECTS/ADVERSE REACTIONS

Side effects rarely occur at the recommended doses. Some patients could have, at the beginning of the treatment, tremor, nervousness, extrasystoles, tachycardia, palpitations, vertigo, anxiety, headache and nausea. In these cases the dose should be reduced.

PRECAUTIONS/WARNINGS

Warnings: Although animal studies have shown no teratogenic effect, clenbuterol should not be given during the first three months of pregnancy.

Precautions: Care must be exercised when additional sympathomimetic agents or IMAO drugs are administered. Clenbuterol should be used with caution in patients with hypertension, coronary heart disease, hyperthyroidism and diabetes. Caution should be used when treating patients with recent cardiac infarction.

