(TSCHAN et al. 1979)	Dose response study of clenbuterol in subjects with obstructive lung disease	12 subjects	6,12, 24 and 48 mcg given qd for 4 days	No side effects noted
(PASOTTI et al. 1979)	Double blind comparison of clenbuterol and salbutamol in subjects with asthma	30 subjects	15 clenbuterol 30 mcg BID for 3days and then 20 mcg BID	No side effects noted
(DI GIOACCHINO et al. 1987)	Open label study of clenbuterol in exercise induced asthma	14 subjects	20 mcg BID for 60 days	Small increase in heart rate
(BRUSASCO et al. 1980)	Single blind cross over study comparing clenbuterol and terbutaline in subjects with chronic airway obstruction	16 subjects	20 to 30 mcg TID for 2 weeks	5 with tremors
(DEL BONO et al. 1979)	Single blind placebo controlled cross over study comparing IV clenbuterol and IV terbutaline in asthmatic subjects	9 subjects	20 mcg daily by IV for 4 days	No adverse reactions were observed with clenbuterol

Incontinence Subjects (Reference)	Study Design	Number of Subjects	Dosage and Regimen	AEs
(GRUNEBERGER 1984)	Controlled double blind study of Flavoxate vs Clenbuterol in motor urge incontinence	39 subjects total 20 subjects in Clenbuterol arm and 19 in Flavoxate arm	20 subjects treated for 6 weeks with 10 mcg clenbuterol three times a day	4 with trembling fingers and tachycardia 3 with nervousness 1 subject stopped due to a drug interaction with an alpha stimulating, antihypertensive drug, clonidine that caused dizziness
(ISHIKO et al. 2000)	Randomized study of clenbuterol and physiological therapy (PT) in stress incontinence	61 subjects assigned to three groups A-clenbuterol only B- PT only C - both	20 mcg BID for 12 weeks in 41 subjects (group A and C)	2 with headache 1 with mild hepatopathy 1 with rash 1 with numbness

7 Study Objectives

Primary Objective

To assess the safety and tolerability of clenbuterol in subjects with ALS

Secondary Objective

To assess the efficacy of clenbuterol with regard to motor function in subjects with ALS

8 Study Design

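### The primary safety endpoint (8.2) is narrower than the primary objective and, with the completer-only population (12.3), leaves subjects who stop early for AEs out of the primary safety result

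*Combined protocol and SAP*

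**What the plan says.** - **Objective (Section 7).** "To assess the safety and tolerability of clenbuterol in subjects with ALS". No dose or period is named.
- **Primary endpoint (8.2).** "The primary endpoint is safety of clenbuterol at 80 mcg BID". The next sentence reads: "Adverse and serious AEs will be systematically gathered as described in section 8 below". That pointer sits inside Section 8 itself; the AE methods are in Section 13.
- **Dosing (8.1).** The start is "40 mcg per oral each morning for one week, followed by 40 mcg BID for the next 5 weeks until the week 6 visit". If that is well tolerated, the next steps are "80 mcg each morning/40 mcg each evening for one week, followed by 80 mcg BID for the next 5 weeks", up to Week 12, and then the same dose to Week 24 if tolerated. Section 10.2 repeats the scheme. The synopsis gives the regimen as a range, 40 to 80 mcg BID.
- **AE collection (13.1.3, 13.2, Section 11).** All AEs are recorded from the first study procedure to 30 days after the last dose. AE review takes place at Weeks 1, 4, 6, 12, 16, 20 and 24.
- **AE analysis (12.2).** A descriptive frequency summary, with no dose restriction.
- **Analysis population (12.3).** Only subjects who finish the study, and only if non-compliance is not documented. No safety population is defined.
- **Tolerability.** The phone visits in 8.1 are meant to assess it, but 8.2, 8.3 and 12.2 define no measure of it.

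**The concern.** An endpoint tied to one dose level describes only subjects who reach that dose, and here reaching it depends on having tolerated a lower one. The protocol's own product information places side effects early: "Some patients could have, at the beginning of the treatment, tremor, nervousness, extrasystoles, tachycardia, palpitations, vertigo, anxiety, headache and nausea". It also says that such effects are rare at recommended doses.

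Section 12.3 adds a second filter. A subject who stops because of an AE is not a completer and so leaves the analysis, whatever the dose at the time. Section 10.5 also withdraws anyone who misses more than 6 doses, so a subject who skips doses because of side effects can be lost by the same route.

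Safety is the primary objective of a single-arm study of 25 subjects. No control group would reveal the selection, and both filters push the result in the favourable direction.

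**Working it through.** **1. The protocol's own timeline.** The steps in 8.1 are 1 + 5 + 1 + 5 = 12 weeks, which reproduces the stated Week 12 visit. Time below 80 mcg BID is 1 + 5 + 1 = 7 weeks, leaving at most 24 − 7 = 17 weeks at 80 mcg BID.

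**2. Share of the study before 80 mcg BID.**
- Weeks: 7/24 = 29%.
- Scheduled administrations: 7×1 + 5×14 + 1×14 = 91. The total is 91 + 17×14 = 329, and 91/329 = 28%.
- Planned cumulative dose: 7×(1×40 + 5×80 + 1×120) = 3,920 mcg. The remainder is 7×17×160 = 19,040 mcg, and 3,920/22,960 = 17%.
- AE review contacts: Weeks 1, 4 and 6, so 3 of 7.

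**3. Who enters the primary safety result.** Section 8.2 can be read as naming a dose level or a target regimen that includes titration. Section 12.3 can be taken to govern safety or not.

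| 8.2 read as | 12.3 applied to safety | Stops for an AE in titration | AE in titration, then completes at 80 mcg BID | Stops for an AE at 80 mcg BID |
|---|---|---|---|---|
| Dose level | Yes | Out | AE out | Out |
| Dose level | No | Out | AE out | In |
| Regimen | Yes | Out | AE in | Out |
| Regimen | No | In | AE in | In |

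Only the last row matches the objective. A subject who stops in titration is lost in the other three, so amending 8.2 or 12.3 alone is not enough. Where 12.3 applies, the proportion stopping for AEs is zero by construction.

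**4. Illustration.** The documents give no rate of stopping in titration, so the number k is assumed. The interval for k/25 is exact (Clopper-Pearson). The upper limit for zero events in n subjects is 1 − 0.025^(1/n).

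| k stopping for AEs in titration | All dosed: k/25 (exact 95% CI) | As written | Upper 95% limit as written |
|---|---|---|---|
| 0 | 0% (0% to 13.7%) | 0/25 | 13.7% |
| 1 | 4% (0.1% to 20.4%) | 0/24 | 14.2% |
| 2 | 8% (1.0% to 26.0%) | 0/23 | 14.8% |
| 3 | 12% (2.5% to 31.2%) | 0/22 | 15.4% |
| 5 | 20% (6.8% to 40.7%) | 0/20 | 16.8% |

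The 13.7% limit at k = 0 reflects the sample size of 25, not this defect. The defect is the gap between the second and third columns.

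**The case against.** The strongest reply is that nothing in the plan discards titration events. They are reviewed at Weeks 1, 4 and 6 and must be recorded. The AE summary in 12.2 carries no dose limit, and the DSMB sees AEs and withdrawals at any dose. Section 6.4 uses 80 mcg BID as shorthand for the selected dose, and 10.2 treats titration as part of the regimen, so 8.2 may simply name the target regimen. Section 12.3 may have been written with efficacy in mind. The synopsis range also allows that a subject could stay on a lower dose and still complete; that subject's AEs would then appear in the summary.

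Much of this stands. A reader might infer that the endpoint counts only AEs at 80 mcg BID and throws away seven weeks of data. The documents do not say so; that is one literal reading of 8.2.

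A reader might also infer that the protocol expects drop-outs in titration. It says only that staging is meant to limit AEs and the attrition they cause. It gives no rate, and 12.1 plans for 25 to enrol and complete.

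Nor does the heart-failure study in Table 1 show titration failure. There, "Two clenbuterol subjects withdrew, one with asymptomatic ventricular tachycardia, and one with muscle cramps without elevated CK", but 40 mcg BID was that study's full dose, reached after 7 days, and the timing of the withdrawals is not given. The Pompe study used a similar staged schedule, and Section 6.4 reports its two dose reductions as coming from the higher dose level.

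What does not stand is the step from collection to endpoint. Recording an AE does not place it in the primary result. No text says that titration AEs belong to that result, and no text exempts safety from 12.3.

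**Conclusion.** The point holds as a conflict between sections that biases the primary safety result. Section 8.2 is narrower than the objective in Section 7 and does not fit the AE period in 13.1.3, and no tolerability measure exists. Section 12.3 is the explicit rule that removes subjects who stop early, and 8.2 read literally reinforces it.

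The period before 80 mcg BID is 29% of the weeks, 28% of the administrations and 17% of the planned cumulative dose. The size of the bias depends on how many subjects stop for AEs, which the documents do not give. With an assumed 2 of 25 stopping in titration, the result reads 0 of 23 rather than 8% (exact 95% CI about 1% to 26%). With none stopping, this source of bias disappears, although 8.2 would still leave unclear whether completers' titration AEs count.

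The conclusion rests on reading 12.3 as covering safety, since it makes no exception, or on reading 8.2 as naming a dose level. The finding does not extend to a claim that titration AEs go uncollected or are certain to be excluded. The change should be made before the data are analysed.

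**What to change.** 1. **8.2:** define the primary safety endpoint as all AEs and SAEs from first dose to 30 days after last dose, at any dose. Correct the cross-reference so that it points to Section 13.
2. **12.3:** add a safety population of every subject who takes at least one dose, and state that the completer rule does not apply to it.
3. **Tolerability:** name a measure, for example the proportion who reach the target dose and remain on it to Week 24, together with discontinuations and dose reductions for AEs.
4. **12.2:** give exact 95% CIs for the main proportions. A table of AEs by dose at onset would keep the information specific to 80 mcg BID; it is helpful but not essential.

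The data are already collected, including from withdrawn subjects, who under 9.4 are called about adverse effects and asked back for a follow-up visit. No change to dosing or visits is involved. The cost is amended wording, one or two extra tables, and a headline AE rate that may look less favourable.

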8.3 Secondary Study Endpoints

Secondary endpoints will include the ALSFRS-R, forced vital capacity (FVC), sniff nasal inspiratory, isometric muscle strength, and sub-maximum handgrip fatigue as described (SHEFNER *et al.* 2016).

9 Subject Selection and Withdrawal

9.1 Inclusion Criteria

1. Diagnosis of possible or more definite ALS according to the El Escorial criteria
2. FVC >50% of predicted for age, height and gender. If FVC testing is restricted due to COVID-19, then a most recent FVC within the past 6 months of 80% or greater will be allowed.
3. At least four of 12 ALSFRS-R questions scored as 2 or 3 at screening.

4. Diminished but measurable grip strength (1) in at least one hand (females:10–50 pounds; males, 10–70 pounds).
5. Taking riluzole at a stable dose or not taking riluzole at screening.
6. On Radicava at a stable dose for at least 30d or not taking this
7. Life expectancy at least 6 months
8. Able to swallow tablets without crushing.
9. Age: 18+ years at enrollment.
10. Subjects are capable of giving written consent.
11. If sexually active, must agree to use contraceptive or abstinence for duration of treatment
12. Females of child bearing age must have negative pregnancy test at screening

9.2 Exclusion Criteria

1. Concurrent illness or laboratory abnormalities that could confound the measurement of ALS progression or interfere with the ability to complete the study.
2. Taking any investigational study drug within 30 days of screening or five half-lives of the prior agent.
3. No previous exposure to clenbuterol.
4. Pregnancy
5. Clinically relevant EKG abnormality (arrhythmia, cardiomyopathy)
6. Tachycardia (resting heart rate greater than 100 beats per minute)
7. History of seizure disorder
8. Hyperthyroidism
9. Pheochromocytoma
10. Pregnancy
11. Have any other co-morbid conditions that in the opinion of the study investigator, places the participant at increased risk of complications, interferes with study participation or compliance, or confounds study objectives
12. History of hypersensitivity to β 2-agonist drugs such as albuterol, levalbuterol (Xopenex), bitolterol (Tornalate), pirbuterol (Maxair), terbutaline, salmeterol (Serevent).
13. The use of the following concomitant meds is prohibited during the study:
 - i. diuretics (furosemide, Lasix)
 - ii. digoxin (digitalis, Lanoxin);
 - iii. β -blockers such as atenolol (Tenormin), metoprolol (Lopressor), and propranolol (Inderal);
 - iv. tricyclic antidepressants such as amitriptyline (Elavil, Etrafon), doxepin (Sinequan), imipramine (Janimine, Tofranil), and nortriptyline (Pamelor);
 - v. MAO inhibitors such as isocarboxazid (Marplan), phenelzine (Nardil), rasagiline (Azilect), selegiline (Eldepryl, Emsam), or tranylcypromine (Parnate); or
 - vi. other bronchodilators such as albuterol (Ventolin), levalbuterol (Xopenex), bitolterol (Tornalate), pirbuterol (Maxair), terbutaline (Brethine, Bricanyl), salmeterol (Serevent), isoetherine (Bronkometer), metaproterenol (Alupent, Metaprel), or isoproterenol (Isuprel Mistometer).

9.3 Subject Recruitment and Screening

Patients from [name] clinic will be approached by study staff to determine their interest in participating in this clinical study. The consent form will be reviewed at the subject's routine clinic visit. Following consent, research study appointments will be made. No compensation is being provided for participation in this study.

9.4 Early Withdrawal of Subjects

When and How to Withdraw Subjects

If the subject decides not to participate or to withdraw from the study, this action will not involve any penalty or loss of benefits to which the subject is entitled, and will not affect the subject's access to health care at Duke. *If the subject* decides to withdraw, the subject will be asked to contact the investigator to notify him. In addition, the subject will be asked to return all unused study drug to the investigator or his staff. The subject will be told about any new information that may affect his or her health, welfare, or willingness to stay in this study.

The investigator may decide to take any subject off this study if his or her condition gets worse, if he or she has serious side effects, or if the investigator determines that it is no longer in the subject's best interest to continue. If the study were halted by the sponsor or a regulatory agent, the subjects will be notified and other options will be discussed.

Data Collection and Follow-up for Withdrawn Subjects

Subjects who withdraw from the study prior to completion of activities will be called in order to determine subject's overall health status and ascertain any adverse effects, and will be asked to return to a follow-up visit for evaluation including medical history, vital signs, and physical examination.

10 Study Drug

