6.4 Dose Rationale and Risk/Benefits

The selected dose (80 mcg BID) is based upon the experience with the long-term administration of clenbuterol, specifically the beneficial muscle effects in a Phase I/II clinical trial that enrolled patients with late-onset Pompe disease who were previously treated with ERT (KOEBERL et al. 2018).

The potential benefits outweigh anticipated risks for daily clenbuterol administration in patients with ALS. Clenbuterol treatment has been associated with specific AEs that may include tremor, muscle cramps, nervousness, and headache (Table 1), as observed in our Phase I/II study in patients with Pompe disease (KOEBERL et al. 2018). Cardiovascular adverse effects of clenbuterol may include palpitations associated with an increase in heart rate. However use of clenbuterol in conservative doses (up to 720 mcg/day) is well tolerated. In a pilot study of patients with congestive heart failure (CHF), clenbuterol was given at 40 mcg twice daily for 12 weeks in 19 patients (n=10 clenbuterol, n=9 placebo) with chronic heart failure in addition to their standard CHF therapy. *The drug was well tolerated and there were no serious AEs in that study.* Only two patients required discontinuation of study drug (one due to asymptomatic slow ventricular tachycardia seen on a 24-hour electrocardiogram and the other due to muscle cramps). Muscle cramps occurred in 6 clenbuterol subjects; only one subject required dose reduction. CK was elevated in 6 clenbuterol subjects (range of peak CK was 300-664 mg/dl, normal range 51-294 mg/dl) and mild tremors were reported in five subjects. No subjects required dose reduction due to elevation of CK or tremors in that study. (KAMALAKKANNAN et al. 2008) In our study in Pompe disease two subjects required dose reduction to 120 mcg from 160 mcg twice daily, due to minor AEs that resolved subsequently (KOEBERL et al. 2018).

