10.5 Subject Compliance Monitoring

Compliance (pill counts) will be measured at the Week 4, Week 12, and Week 24 visits. The subject will have phone visits during Week 1, 7, 12, 16 and 20, and compliance will be discussed then. Subjects who miss >6 doses of the study drug, will be considered non-compliant and withdrawn from the study ([Table 3](#)).

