10.9.4 Return or Destruction of Study Drug

Unused drug will be destroyed by the Investigational Drug Service at the end of the study.

At the completion of the study, there will be a final reconciliation of drug shipped, drug consumed, and drug remaining. This reconciliation will be logged on the drug reconciliation form, signed and dated. Any discrepancies noted will be investigated, resolved, and documented prior to return or destruction of unused study drug. Drug destroyed on site will be documented in the study files.

11 Study Procedures

1. Research Activities: Medical History: Reviewed prior to study drug initiation.
2. Vital Signs: Completed at Screening/Baseline, Week 4, Week 12, and Week 24.
3. Physical Examination: Performed at Screening/Baseline, Week 4, Week 12, and Week 24.
4. AE Review: Completed at Week 4, Week 12, Week 24, and telephone visits.
5. Blood Samples: Blood samples will be obtained at Screening/Baseline, Week 4, Week 12, and Week 24. for the following analyses:
 - Safety Labs: Hematology and Chemistry (5 ml) to consist of:
 - a. Complete Blood Count (CBC)
 - b. Chemistry panel (including electrolytes, BUN, creatinine, glucose)
 - c. Liver panel (including albumin, aspartate aminotransferase (AST), alanine aminotransferase (ALT), and total bilirubin)
 - d. Creatine kinase (CK)
6. Electrocardiogram: Performed at Screening/Baseline, Week 4, Week 12, and Week 24.
7. Forced Vital Capacity (FVC) Testing: Performed at Screening/Baseline, Week 4, Week 12, and Week 24
8. ALSFRS-R: Performed at Screening/Baseline, Week 4, Week 12, Week 16, Week 20 and Week 24.
9. Muscle strength testing: Myometer testing (SORARU *et al.* 2006) and isometric muscle strength, and sub-maximum handgrip fatigue (SHEFNER *et al.* 2016), performed at Screening/Baseline, Week 4, Week 12, and Week 24.
10. Telephone visits: Performed during Week 1, 6, 16 and 20.
11. Serum pregnancy testing at Screening/Baseline. Urine pregnancy testing at Weeks 4, 12 and 24.
12. Thyroid function (T4, TSH) at Screening/Baseline.

Table 3: Testing Schedule

	Screening/ Baseline (Week 0)	Phone Visit (Week 1)	Study Visit (Week 4)	Phone Visit (Week 6)	Study Visit (Week 12)	Phone Visit (Week 16)	Phone Visit (Week 20)	Final Visit (Week 24)
Medical History	X							
Vital Signs	X		X		X			X
Physical Exam	X		X		X			X
Obtain Consent	X							
Study Drug Dispensed	X		X		X			
AE Review		X	X	X	X	X	X	X
Blood Sample	X				X			X
Safety testing	X		X		X			X
Thyroid function testing	X							

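### Section 9.4 does not require an EKG or safety labs (including CK) at withdrawal, so subjects who leave early may have no recent test, or none at the target dose

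*Combined protocol and SAP*

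**What the plan says.** Section 9.4 provides that subjects who withdraw are called about their health and any adverse effects, and that each "will be asked to return to a follow-up visit for evaluation including medical history, vital signs, and physical examination". The investigator may take a subject off study for worsening condition or "if he or she has serious side effects". Section 10.5 adds a further route out: "Subjects who miss >6 doses of the study drug, will be considered non-compliant and withdrawn from the study".

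Section 11 fixes when the objective safety tests are done. Item 6 reads "Electrocardiogram: Performed at Screening/Baseline, Week 4, Week 12, and Week 24". Item 5 reads "Blood samples will be obtained at Screening/Baseline, Week 4, Week 12, and Week 24", and the panel it lists includes CK. Table 3 has columns for the scheduled visits and calls only, with none for early withdrawal.

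Section 8.2 states: "The primary endpoint is safety of clenbuterol at 80 mcg BID". Section 12.3 limits the analysis to completers with no documented non-compliance and names no separate safety population.

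**The concern.** In a single-arm study whose primary endpoint is safety, the assessment at the end of treatment should not depend on whether the subject reached Week 24. Here a completer must have an EKG and a full safety panel at the last visit. A subject who stops early need have only a history, vital signs and an examination. An EKG change, a CK rise or another laboratory abnormality without symptoms can pass through that visit unseen. Because the tests are optional at exit, they will probably be done for some withdrawn subjects and not for others, and the resulting rates will be hard to interpret.

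**Working it through.** The plan gives no figure on this point to reproduce. The check compares the schedule with the dose steps and then sizes the group affected.

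**1. Last required test by time of withdrawal.** Dose steps are from Sections 8.1 and 10.2, assuming escalation on schedule. Test weeks are from Section 11.

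| Withdrawal | Highest scheduled dose by then | Last required EKG and CK | Longest age of that test at exit |
|---|---|---|---|
| Weeks 0 to 4 | 40 mcg BID | Week 0, before drug | 4 − 0 = 4 weeks |
| Weeks 4 to 6 | 40 mcg BID | Week 4, on 40 mcg BID | 6 − 4 = 2 weeks |
| Weeks 6 to 12 | 80 mcg BID (from Week 7) | Week 4, on 40 mcg BID | 12 − 4 = 8 weeks |
| Weeks 12 to 24 | 80 mcg BID | Week 12 | 24 − 12 = 12 weeks |

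The third row matters most: up to five weeks at 80 mcg BID with no required EKG or CK above 40 mcg BID. Table 3's blood-sample row has no mark at Week 4, although its safety-testing row does. I have followed Section 11, which lists Week 4.

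**2. Whether another section supplies the tests.**
- 13.1.3 sets a 30-day reporting window and attaches no test to it.
- 13.1.6 follows events that are already known.
- 13.1.7 says when a laboratory abnormality counts as an adverse event, which presupposes a sample.
- 13.2 asks for questioning, with examination where appropriate.
- 13.6.1 has the DSMB review EKGs and withdrawals but orders nothing at exit.

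None of them requires an EKG or blood test at withdrawal.

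**3. What the cited heart-failure study shows.** Section 6.4 reports two discontinuations, "one due to asymptomatic slow ventricular tachycardia seen on a 24-hour electrocardiogram and the other due to muscle cramps". CK rose in 5 clenbuterol subjects (Table 1) or 6 (Section 6.4), and in 4 placebo subjects (Table 1). According to Table 1, the subject who stopped for cramps had no CK elevation.

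**4. Expected number leaving early.** Early-stop rates in the studies the protocol cites, applied to N = 25:
- ALS pilot: 25 × 2/16 = 3.1
- Pompe study: 25 × 2/13 = 3.8
- Heart-failure study: 25 × 2/10 = 5.0 or 25 × 2/9 = 5.6 (Section 6.4 gives 10 clenbuterol subjects, Table 1 gives 9)

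That is about 3 to 6 subjects, leaving 22 to 19 with the full set of tests.

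**5. Effect on detection (illustration).** The chance of seeing at least one abnormality is 1 − (1 − p)^n, where p is an assumed true rate.
- p = 5%: 72.3% with n = 25, against 67.6% (n = 22) to 62.3% (n = 19)
- p = 10%: 92.8% with n = 25, against 90.2% to 86.5%

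If no event is seen, the one-sided 95% upper bound is 1 − 0.05^(1/n): 11.3% with n = 25, against 12.7% (n = 22) to 14.6% (n = 19).

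These figures treat withdrawal as unrelated to toxicity and count a withdrawn subject as contributing no test. The second assumption overstates the loss, because anyone leaving after Week 4 has at least one on-drug test. If withdrawn subjects had more events, the loss would be larger than this calculation shows.

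**The case against.** The strongest reply is that Section 9.4 sets a minimum. Its list is introduced by the word including, so an investigator may order an EKG or CK at exit. That is correct, and a reader who inferred that the protocol excludes these tests would go too far. What remains is that they are not required.

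A reader might also infer that withdrawn subjects are the ones most likely to have cardiac or muscle toxicity, so that the abnormalities are lost where they are commonest. The documents do not show this. No reasons are given for non-completion in the ALS pilot or the Pompe study. In the heart-failure study CK also rose on placebo, and the one withdrawal for cramps came without a CK rise. Subjects may also leave this trial for missed doses or worsening disease.

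Nor do the documents show that an exit EKG would have found the cited ventricular tachycardia. It was seen on a 24-hour recording, and Section 11 gives no sign that its EKG is of that kind. That event was the reason for stopping, not something missed because the subject stopped.

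Recognised events are covered: they are followed up, SAEs reach the DSMB Chair within 24 hours, and calls at Weeks 16 and 20 review adverse events. Vital signs can show tachycardia, and questioning can bring out cramps or palpitations. These points narrow the gap to silent abnormalities but do not close it.

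The attrition rates are weak inputs. The Pompe figure covers all randomized subjects over 52 weeks, and the heart-failure figure comes from another disease over 12 weeks.

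**Conclusion.** The point holds as a gap in required data collection. The schedule result follows from the text and needs only the assumption of on-time escalation. The estimate of 3 to 6 early leavers assumes attrition like that in three small cited studies. The detection loss is modest, roughly 5 to 10 percentage points at an assumed 5% rate (72.3 − 67.6 = 4.7; 72.3 − 62.3 = 10.0), and smaller still if earlier tests are counted.

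It would be wrong to conclude that the safety results will be biased downward: that needs a higher rate of silent abnormality among withdrawn subjects, which is plausible but undocumented. The supportable conclusion is that such abnormalities may be missed or gathered unevenly. Section 12.3 adds to this, because exit tests from non-completers may not enter the analysis even when they are done. The change is worth making because it is cheap and bears on the primary endpoint.

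**What to change.** Add an early-withdrawal column to Table 3 containing the Week 24 safety assessments: vital signs, physical exam, EKG, safety labs with CK, and a urine pregnancy test where applicable. Hold the visit as close as feasible to the last dose, and replace the list in 9.4 with a reference to that column. Pulmonary function and ALSFRS-R may be added but are not needed for this point.

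Amend 12.3 so that safety, including EKG and CK, is reported for all dosed subjects and not only for compliant completers. Without this the extra data may not be used.

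Separately, reconcile the heart-failure study's arm sizes and CK counts between Table 1 and Section 6.4; the point does not depend on them.

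The cost is one table column, short edits to two sections and a longer exit visit that some withdrawn subjects may decline. The procedures are already planned for Week 24, and no dosing or stopping rule changes.
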